**A Pharmacodynamic study comparing prasugrel versus ticagrelor in patients with coronary
artery disease undergoing PCI with CYP2C19 loss-of-function genotypes:
A feasibility study with point-of-care pharmacodynamic and genetic testing**

Investigators

[name], PhD

[name]

[name]

[name], BSN

Project Overview

Clopidogrel is the most broadly utilized platelet P2Y₁₂ receptor inhibitor. However, numerous studies have shown that pharmacodynamics (PD) response profiles vary among clopidogrel treated patients and that individuals with reduced response have an increased risk of recurrent ischemic events. There are multiple factors contributing to clopidogrel response variability. Among these, genetic variations of the cytochrome P450 (CYP) 2C19 enzyme, a key contributor to clopidogrel metabolism, have been involved. In particular, loss-of-function (LOF) alleles of the CYP2C19 enzyme reduce transformation of clopidogrel pro-drug into its active metabolite. Thus, patients carrying LOF alleles have lower levels of clopidogrel's active metabolite as well as diminished platelet inhibition, which translates into an increased rate of adverse cardiovascular events, particularly in the setting of percutaneous coronary intervention (PCI). Because of these findings, drug regulating authorities have provided a boxed warning on the product label of clopidogrel on the potential for reduced efficacy of clopidogrel among CYP2C19 LOF carriers and suggested considering alternative antiplatelet therapies for these individuals. Prasugrel and ticagrelor are novel generation P2Y₁₂ receptor inhibitors characterized by greater PD potency and reduced ischemic event rates compared with clopidogrel, and are not affected by CYP2C19 LOF polymorphisms. However, to date there are limited head-to-head PD comparisons between these two new P2Y₁₂ receptors blockers, and there are no studies assessing on how these agents behave among CYP2C19 LOF carriers. Tailoring antiplatelet therapy according to results of genetic testing has been limited in real world clinical practice because of not having readily accessible results of individual's genetic makeup. The aim of the present study is to compare the PD effects of prasugrel versus ticagrelor in patients undergoing PCI with CYP2C19 LOF alleles using the novel point-of-care genetic testing *Spartan RX-CYP2C19* which permits accurate and rapid identification of CYP2C19 genetic status.

Background and Significance:

Dual antiplatelet therapy consisting of aspirin and clopidogrel is the cornerstone of treatment for prevention of thrombotic events in patients with coronary artery disease (CAD) who have an acute coronary syndrome (ACS) or undergo percutaneous coronary intervention (PCI) [1]. However, there are a considerable number of patients who continue to have recurrent ischemic events despite this treatment regimen [2,3]. In fact, variability in the pharmacodynamic (PD) response to clopidogrel is well recognized, and patients with high on-treatment platelet reactivity (HPR) are at increased risk of adverse cardiovascular events [4]. Variability in clopidogrel response is a multifactorial process. One of the contributing factors is the variability in its metabolism. Clopidogrel is a prodrug and needs to undergo biotransformation to become an active metabolite to exert its antiplatelet effects. Clopidogrel is metabolized by the hepatic cytochrome P450 (CYP) system in two steps and CYP 2C19 is involved in both steps [5]. Multiple studies have demonstrated that both heterozygotes and homozygotes for loss-of-function (LOF) alleles have lower levels of the active clopidogrel metabolite as well as diminished platelet inhibition [6]. Moreover, carriers of any LOF allele have an increased rate of cardiovascular adverse events, particularly in the setting of PCI [7]. Because of these findings, drug regulating authorities have provided a boxed warning on the product label of clopidogrel on the potential for reduced efficacy of clopidogrel among CYP2C19 LOF carriers and suggested considering alternative antiplatelet therapies, which include prasugrel and ticagrelor, for these individuals [8,9]. However, to date there are no head-to-head comparisons between these agents among CYP2C19 LOF carriers.

Recently, new P2Y₁₂ receptor blockers, prasugrel and ticagrelor, have been approved for clinical use [10,11]. Both new P2Y₁₂ receptor antagonists have more potent PD effects compared with clopidogrel, which has translated into better clinical outcomes in patients with ACS [12,13]. The PD

effects of both drugs have not shown to be affected by CYP2C19 genetic status and both agents achieve more potent platelet inhibitory effects than clopidogrel in healthy volunteers with CYP2C19 LOF alleles [6,14]. These PD findings have also been shown in patients with CAD and post-hoc analyses of two large, international trials have not shown any clinical interaction between ticagrelor or prasugrel and CYP2C19 LOF polymorphisms [15-20]. However, to date there are no head-to-head PD comparisons between these two new P2Y₁₂ receptors blockers among patients with CYP2C19 LOF alleles. Tailoring antiplatelet therapy according to results of genetic testing has been limited in real world clinical practice of patients undergoing PCI by having readily accessible results of individual's genetic makeup. Recently, a new point-of-care genotyping assay for the CYP2C19 LOF polymorphisms, *Spartan RX*, has been developed and approved by the Food and Drug Administration (FDA) as a feasible bedside tool [21,22]. The Rapid Gene study showed that point-of-care genetic testing permits accurate identification of CYP2C19 LOF carriers. Moreover, the use of *Spartan RX* as genetic testing may facilitate the rapid personalization of anti-platelet therapy as demonstrated with the reduction of HPR in the rapid genotyping group using prasugrel on those patients who showed to be LOF carriers [18,20]. The present investigation will compare the PD effects of prasugrel and ticagrelor in PCI-treated patients with CYP2C19 LOF using the *Spartan RX* device.

Specific Aim and study hypothesis:

The primary aim of the present study is to compare the PD effects of prasugrel and ticagrelor in patients undergoing PCI presenting with CYP2C19 LOF alleles. The study hypothesis is the non-inferiority in platelet reactivity at 24 hours of prasugrel versus ticagrelor among LOF allele carriers.

Research Design and Methods:

Research design

Patients scheduled for left heart catheterization (LHC) with intent to undergo PCI will be screened for the study. Patients will be screened in our inpatient and outpatient services referring patients to our cardiac catheterization laboratories to undergo LHC. Patients must fulfill all specific inclusion and exclusion criteria described below. A rapid genetic testing using the point-of-care genotyping (*Spartan RX*) will be performed in these patients to define carriers of LOF alleles. In particular, this point-of-care assay enables assessment of the following alleles: *1,*2,*3 and *17. The most common LOF alleles are *2 and *3. Therefore, carriers of *2 or *3 LOF carrier status [homozygotes (*2/*2, *3/*3 or *2/*3) or heterozygotes (*1/*2, *1/*3, *2/*17, *3/*17)] will be eligible for randomization. Patients who are non-carriers of LOF alleles (*1/*1, *1/*17 or *17/*17) will not be eligible for randomization and considered as screen failures and treated per standard of care. Also, screened patients with CYP2C19 LOF alleles who do not undergo PCI will be considered as screen failures and treated per standard of care.

Screened patients, either on aspirin monotherapy or on dual antiplatelet therapy (DAPT) with aspirin and clopidogrel as per standard of care, defined to be carriers of LOF and undergoing PCI will be randomized. Patients will be randomly (1:1 randomization) assigned to receive FDA approved doses of either prasugrel (60 mg loading dose - 10 mg/day maintenance dose) or ticagrelor (180 mg loading dose - 90 mg b.i.d maintenance dose). Randomization will be stratified according to baseline antiplatelet therapy (aspirin alone vs. DAPT with aspirin and clopidogrel). Loading dose administration will be given immediately after PCI as per standard of care. Maintenance dose will be

maintained for up to 30 days. Afterwards, patients will continue with the antiplatelet therapy recommended by the treating cardiologist (clopidogrel, prasugrel or ticagrelor).

Study Population

• Inclusion criteria:

1. Patients scheduled for left heart catheterization and undergoing PCI
2. Age 18-75 years
3. On aspirin (81mg) monotherapy or on DAPT with aspirin (81mg) and clopidogrel (75mg) as per standard of care
4. Presence of at least one 2C19 LOF allele

[figure not shown]
• Exclusion criteria:

1. Known allergies to aspirin, prasugrel, ticagrelor, or clopidogrel
2. Age >75 years
3. Weight <60kg
4. Considered at high risk for bleeding
5. History of ischemic or hemorrhagic stroke or transient ischemic attack
6. Known severe hepatic dysfunction
7. On treatment with oral anticoagulant therapy (Vitamin K antagonists, dabigatran, apixaban, rivaroxaban)
8. Use of glycoprotein IIb/IIIa inhibitors (abciximab, eptifibatide, tirofiban)
9. Blood dyscrasia or bleeding diathesis
10. Platelet count <80x10⁶/mL

11. Hemoglobin <10 g/dL.
12. Active bleeding or hemodynamic instability
13. Creatinine Clearance <30 mL/minute
14. Patients with sick sinus syndrome (SSS) or high degree AV block without pacemaker protection.
15. Current treatment with drugs interfering with CYP3A4 metabolism (to avoid interaction with Ticagrelor): Ketoconazole, itraconazole, voriconazole, clarithromycin, nefazodone, ritonavir, saquinavir, nelfinavir, indinavir, atazanavir, and telithromycin.
16. Pregnant females*

*Women of childbearing age must use reliable birth control (i.e. oral contraceptives) while

participating in the study. The study design is detailed in the following figure.

Blood sampling

In patients meeting study entry criteria and undergoing PCI, blood sampling will be performed at 5 time points: a) baseline (prior to initiating the PCI procedure and loading dose administration of antiplatelet therapy); b) 30 minutes after loading dose administration; c) 2 hours after loading dose administration; d) 24 hours after loading dose administration or hospital discharge (whichever comes first); e) during routine follow-up clinical visit 1 – 4 weeks after PCI while on maintenance dose antiplatelet therapy. Time points will have a 10% window.

Genetic Testing

Spartan RX point-of-care rapid genotyping: Spartan RX (Spartan Bioscience Inc., Ontario, Canada) is the point-of-care determining the CYP2C19 (*1,*2,*3,*17) allele status within 1 hour. This test consisted of four separate steps intended to be done in less than 8 minutes: acquisition of a buccal swab; insertion of the swab into the cartridge; insertion of the reaction solution into the device; and analysis of CYP2C19 genotype triggered by a button on the device. In this study, patients with the *2 or *3 LOF carrier status [homozygotes (*2/*2, *3/*3 or *2/*3) or heterozygotes (*1/*2, *1/*3,

*2/*17, *3/*17)] will be eligible for randomization. Patients who are non-carriers of LOF alleles (*1/*1, *1/*17 or *17/*17) will be treated per standard of care [21].

Platelet Function Assays:

VerifyNow Point-of-care Testing: The VerifyNow System is a turbidimetric based optical detection system which measures platelet induced aggregation as an increase in light transmittance (Accumetrics, San Diego, CA) and will be utilized according to manufacturer's instructions [23]. The assay is based on microbead agglutination and uses specific reagents for the pathways of interest. The instrument measures this change in optical signal and reports results in P2Y₁₂ Reaction Units (PRU). High on-treatment platelet reactivity (HPR) is defined by PRU >208 [4].

Study Endpoints and Determination of Sample Size:

The primary endpoint is the non-inferiority in platelet reactivity, measured as PRU, at 24 hours or hospital discharge (whichever comes first) of prasugrel versus ticagrelor among LOF allele carriers in each cohort. Under the assumption of 0 difference in mean PRU between treatments and a common standard deviation of 50 PRU, a sample size of 60 patients will allow for the 95% CI to stay within ± 40 PRU with a 85% power and $\alpha=0.025$. Considering a 25% rate of invalid results due to hemolysis or drop-out (based on our prior experience), we will randomize a total of 80 patients to ensure complete data for analysis. Non-inferiority will be assessed using a 95% CI of the difference in mean PRU between the 2 groups. Secondary endpoints will include: differences in PRU between prasugrel and ticagrelor at 30 minutes, 2 hours, and 1-4 weeks (during maintenance therapy); rates of HPR at all study time points. Subgroup analyses will be performed according to baseline antiplatelet therapy (aspirin alone vs. DAPT with aspirin and clopidogrel)

Statistical Analysis:

Continuous variables will be expressed as a mean \pm SD or median [IQR] as appropriate. Categorical variables will be expressed as frequencies and percentages. Comparisons between continuous variables will be performed using Student t-test or Wilcoxon rank-sum test. Comparisons between categorical variables will be performed using McNemar test or binomial exact test. Missing data will not be imputed. An analysis of covariance method with a general linear model, with treatment as the main effect and baseline values of platelet reactivity as a covariate, will be used to evaluate the primary endpoint as well as all between-group comparisons at each time point. Least squares mean (LSM) differences in PRU between groups and the corresponding 2-sided 95% CI for the difference will be obtained based on the analysis of covariance model. The PD population will include all patients with PD data and without a major protocol deviation thought to affect significantly the PD effects of ticagrelor or prasugrel. The PD population will be used for analysis of all primary and secondary PD variables. Erroneously treated patients (e.g., those randomized to one treatment but actually given the other) will be accounted for based on the actual treatment received. Statistical analysis will be performed by our group using SPSSv24.0 software (SPSS Inc. Chicago, IL).

Possible Discomforts and Risk

In clinical trials, the most common clinical side effects of prasugrel were blurred vision, dizziness, headache, nervousness; infrequent events included intracranial hemorrhage (0.79%) and severe neutropenia (< 0.1%). The most important adverse effect associated with the use of prasugrel is bleeding [11]. The risk of non-surgical bleeding is 2.4%. On the other hand, the most common clinically side effects of ticagrelor were dyspnea (13.8%), headache (6.5%), cough (4.9%), dizziness

(4.5%), and nausea (4.3%), principally. Also, the most important adverse effect associated with the use of ticagrelor is bleeding [10]. The risk of non-surgical bleeding is 2.8%. All clinical events, if they were to occur, including myocardial infarctions both fatal and non-fatal, strokes, peripheral vascular disease, bypass surgery (coronary or peripheral vascular), repeated hospitalizations, and bleeding will be recorded. Clinical events will be evaluated by a local committee, comprised of 3 faculty members (2 cardiologists and 1 non-cardiologist), not directly involved in the research. In the event of a report of a serious adverse event (major bleeding – defined as life-threatening: fatal, symptomatic intracranial hemorrhage, leading to a drop in hemoglobin of at least 5 g/dL, significant hypotension requiring intravenous inotropes, requiring surgical intervention, or requiring transfusion of 4 or more units of blood; non–life-threatening: substantially disabling, intraocular bleeding leading to vision loss, or requiring at least 2 units of blood; thrombocytopenia $<50,000$), the local committee will meet and antiplatelet treatment will be withdrawn.

Definition of Adverse Events

An adverse event is any unintended or undesirable experience that occurs during the course of the clinical investigation whether or not it is considered to be therapy related. This includes any newly occurring event or previous condition that has increased in severity or frequency since the initiation of study treatment. Adverse events will be followed until resolution while the patient remains on-study. Once the patient is removed from study, events thought to be related to the study therapy will be followed until resolution or until the patient starts a new treatment regimen.

Serious Adverse Events (SAE): An adverse event occurring while on study and considered related (reasonable possibility that the study treatment caused the adverse experience) to the study treatment that results in any of the following outcomes:

- Death
- A life-threatening adverse experience.
- A persistent or significant disability, incapacity, or is a congenital anomaly, or birth defect.
- Requires inpatient hospitalization, or prolongation of existing hospitalization.

The definition of serious adverse event also includes ‘important medical event’. Medical and scientific judgment should be exercised in deciding whether expedited reporting is appropriate in other situations, such as important medical events that may not be immediately life-threatening or result in death or hospitalization but may jeopardize the patient and/or may require medical or surgical intervention to prevent one of the other outcomes listed in the definition above. These should also usually be considered serious. Examples of such events are intensive treatment in an emergency room or at home for allergic bronchospasm; blood dyscrasias or convulsions that do not result in hospitalization; or development of drug dependency or drug abuse.

Possible benefits

The present investigation is aimed to evaluate the PD differences between ticagrelor and prasugrel in patients with CYP2C19 LOF alleles. Although, this study is not designed to evaluate differences in clinical outcomes, the results obtained may prompt further large scale clinical investigation.

Potential Financial Risks

None

Potential Financial Benefits

None

Conflict of Interest

[name] is a consultant for Bristol Myers Squibb/Sanofi-Aventis, the makers of clopidogrel (Plavix), Eli-Lilly/Daiichi-Sanyo, the makers of prasugrel (Effient), and Astra Zeneca, the makers of ticagrelor (Brilinta).

References:

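### The 85% power belongs to one-sided non-inferiority, but the criterion written (95% CI within ±40 PRU) is two-sided equivalence, with about 72–75% power at 60 patients

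*Combined protocol and SAP*

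**What the plan says.** Under Specific Aim and study hypothesis, the protocol states: "The study hypothesis is the non-inferiority in platelet reactivity at 24 hours of prasugrel versus ticagrelor among LOF allele carriers". The section Study Endpoints and Determination of Sample Size frames the primary endpoint as non-inferiority too.

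That section assumes no true difference and "a common standard deviation of 50 PRU", then says that "a sample size of 60 patients will allow for the 95% CI to stay within ± 40 PRU with a 85% power", with α given as 0.025. Allowing for 25% invalid results or drop-out, 80 patients are to be randomised. This is the only place where a margin appears.

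The same paragraph then says: "Non-inferiority will be assessed using a 95% CI of the difference in mean PRU between the 2 groups". It names no limit, sign or margin. The Statistical Analysis section specifies a two-sided 95% CI for the least squares mean difference from an ANCOVA adjusted for baseline platelet reactivity, again with no decision rule.

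**The concern.** Non-inferiority on PRU, where higher means less platelet inhibition, concerns one limit: prasugrel's mean must not exceed ticagrelor's by 40 or more. A criterion of "95% CI to stay within ± 40 PRU" concerns both limits and is equivalence. The two criteria have different power at the same sample size, so one power figure cannot serve both.

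The two rules can also reach opposite conclusions on the same data. If prasugrel lowered PRU well below ticagrelor, the lower limit could pass −40. The written rule would then fail, although the result is the opposite of a non-inferiority failure. Because no other sentence gives the rule, the choice between the readings could be made after the data are seen.

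**Working it through.** **Inputs, all from the protocol.** True difference 0, SD 50 PRU, margin 40 PRU, α = 0.025 and a 95% CI, 60 evaluable patients and 25% loss (Study Endpoints and Determination of Sample Size); 1:1 allocation (Research design). Hence 30 evaluable per arm. The difference is taken as prasugrel minus ticagrelor.

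**Standard error.** SE = 50 × √(2/30) = 12.91, and 40/12.91 = 3.098.

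**1. Reproducing the plan's figure as one-sided non-inferiority (upper limit below +40).**
- Normal: Φ(3.098 − 1.960) = Φ(1.138) = 0.873.
- Noncentral t, 58 df: 0.861.
- By t, 29 per arm gives 0.849 and 30 gives 0.861, so 30 per arm is the smallest size that reaches 85%. That is the stated 60.
- Randomised: 60/(1 − 0.25) = 80, as stated.

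**2. The criterion as written (both limits within ±40).**
- Normal: 2Φ(1.138) − 1 = 0.745.
- t, integrating over the sampling distribution of the SD: 0.723. A simulation of 400,000 trials gave 0.724.
- Shortfall against 85%: about 10 to 13 percentage points.

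**3. Sample size for 85% power on the criterion as written.**

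| Evaluable per arm | Normal | t |
|---|---|---|
| 30 | 74.5% | 72.3% |
| 37 | 86.1% | 84.9% |
| 38 | 87.3% | 86.2% |

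So 37 (normal) or 38 (t) per arm are needed, that is 74 or 76 evaluable. Randomised: 74/0.75 = 98.7, rounded up to 99; 76/0.75 = 101.3, rounded up to 102.

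**4. How far the two rules diverge.** The expected half-width of the CI is 2.002 × 12.91 = 25.8 PRU. At that width, the ±40 rule fails for any observed difference below −40 + 25.8 = −14.2. For illustration, assume prasugrel is truly 20 PRU lower; the protocol does not posit this. By t, one-sided non-inferiority then succeeds 99.5% of the time and the ±40 rule 33%.

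**The case against.** The strongest reply is that this is a slip of wording. The plan speaks of non-inferiority throughout, α = 0.025 is the usual one-sided level, and on that reading 60, 85% and 80 all reproduce. The ± sign sits in a planning sentence, not in the sentence on assessment. Much of this stands: the trial is not underpowered for its stated hypothesis. But the assessment sentence gives no limit or margin, so the planning sentence is the only statement of the rule, and it describes a different test from the one its power figure fits.

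Three narrower objections:

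- **Another origin for the 85%.** Two one-sided tests at 0.05, that is a 90% CI within ±40, give 84.4% (t) or 85.4% (normal) at 30 per arm. The plan does not document where its figure comes from. The stated 95% CI and α = 0.025 exclude this route.
- **Gain from ANCOVA.** If 50 is the unadjusted SD, adjusting for baseline raises power. Assumed baseline correlations of 0.3 and 0.5 would give about 80% and 89% (normal) for the ±40 rule. The plan states no correlation and does not say whether 50 is a raw or residual SD, so this gain cannot be credited. It does make 72–75% conditional on SD 50 being the SD that applies.
- **All 80 evaluable.** With 40 per arm the ±40 rule would have 88–89% power. But the plan attaches its 85% to 60 patients and expects to lose 25%.

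**Conclusion.** The concern holds. The stated 85% fits one-sided non-inferiority at 0.025 (86.1% by t, 87.3% normal). The criterion to which the plan attaches it has 72.3% (t) or 74.5% (normal). These figures rest on the plan's inputs: 30 evaluable per arm, SD 50, true difference 0, a 95% CI, and no gain from the baseline covariate. The fault is an inconsistency between rule and power. It must be corrected because it leaves the primary success criterion undetermined.

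**What to change.** Replace the sample-size sentence with wording such as: *Non-inferiority is declared if the upper limit of the two-sided 95% CI for the ANCOVA least squares mean difference (prasugrel minus ticagrelor) is below +40 PRU; with 60 evaluable patients, SD 50 and true difference 0, power is about 86%.* Say also whether 50 is the raw or residual SD; the 86% is an unadjusted two-sample figure and carries over to the ANCOVA if 50 is the residual SD. The cost is this text edit; 60 evaluable and 80 randomised are unchanged.

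If equivalence within ±40 is really intended, keep the rule, name it equivalence in the hypothesis and endpoint, and restate the power as about 72%. No patients are added if that power is accepted; holding 85% would take about 99–102 randomised. Either way, settle the wording before treatment-group results are seen.

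### The plan names no suitable test for comparing rates of high platelet reactivity (HPR) between the two independent arms

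*Combined protocol and SAP*

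**What the plan says.** Under Research design the trial has two parallel arms: "Patients will be randomly (1:1 randomization) assigned to receive" one of the two drugs. The only structure imposed on the allocation is by stratum: "Randomization will be stratified according to baseline antiplatelet therapy". Individual patients are not matched.

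Under Study Endpoints and Determination of Sample Size, the secondary endpoints include "rates of HPR at all study time points". HPR is binary and is defined under Platelet Function Assays as PRU above 208. Under Blood sampling, "blood sampling will be performed at 5 time points", so each patient contributes repeated HPR readings.

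The Statistical Analysis section gives one rule for categorical data: "Comparisons between categorical variables will be performed using McNemar test or binomial exact test". It does not say which comparison each test serves. A separate sentence says that a covariance model with baseline platelet reactivity as covariate "will be used to evaluate the primary endpoint as well as all between-group comparisons at each time point", but the stated output of that model is a least squares mean difference in PRU. Fisher's test, chi-square, logistic regression and stratified tests for proportions are not mentioned anywhere.

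**The concern.** McNemar's test uses discordant pairs. Across two independently randomised arms there are none, and forming them by hand makes the p-value depend on the pairing chosen. A binomial exact test could mean the exact form of McNemar, a one-sample test, or a test of how the HPR patients split between the arms. Only the last is a sound between-arm comparison, and the plan does not state it.

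The test behind any claim about HPR rates would therefore be chosen later, possibly after the data are seen, and the candidate tests can fall on different sides of 0.05.

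**Working it through.** **Inputs.** The plan states 60 evaluable patients, 80 randomised, 1:1 allocation and a 25% loss ("Considering a 25% rate of invalid results due to hemolysis or drop-out"). It states no HPR rates, margin or power for HPR, so every HPR count and rate below is an assumption. All tests are two-sided at 0.05 and all results are exact enumerations.

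**The plan's own figures.** Non-inferiority with margin 40, SD 50, true difference 0, one-sided alpha 0.025 and power 85% needs n per arm = 2 × [50 × (1.960 + 1.036) / 40]² = 28.1, rounded up to 29, or 58 in total. The stated 60 agrees to within 2 patients. 60 / (1 − 0.25) = 80, as stated. This gives 30 evaluable per arm.

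**One data set, three readings.** Assume HPR in 13/30 against 5/30.

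- Fisher's exact test: p = 0.047.
- Split binomial (13 of the 18 HPR patients in one arm, tested against 0.5 because the arms are equal): 2 × (8568 + 3060 + 816 + 153 + 18 + 1) / 2¹⁸ = 2 × 12616 / 262144 = 0.096.
- Exact McNemar across arms: if k pairs have HPR in both members, the discordant counts are 13 − k and 5 − k, and p = 2 × P(X ≥ 13 − k), with X ~ Binomial(18 − 2k, 0.5). Under random pairing k is hypergeometric.

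| k | Discordant pairs | Probability of k | McNemar p |
|---|---|---|---|
| 0 | 13 / 5 | 0.043 | 0.096 |
| 1 | 12 / 4 | 0.217 | 0.077 |
| 2 | 11 / 3 | 0.372 | 0.057 |
| 3 | 10 / 2 | 0.273 | 0.039 |
| 4 | 9 / 1 | 0.085 | 0.021 |
| 5 | 8 / 0 | 0.009 | 0.008 |

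The probability of p ≤ 0.05 is 0.273 + 0.085 + 0.009 = 0.367, so 63% of pairings give p > 0.05.

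**Patients left out by cross-arm pairing.** With 40 randomised per arm and each patient independently evaluable with probability 0.75, the arms have equal evaluable numbers in about 10% of trials and differ by 3.1 patients on average. Pairing would usually discard someone.

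**Type I error, 30 per arm.**

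| True HPR in both arms | Fisher | Split binomial | McNemar, random pairing |
|---|---|---|---|
| 10% | 0.009 | 0.009 | 0.010 |
| 20% | 0.022 | 0.012 | 0.022 |
| 30% | 0.026 | 0.010 | 0.025 |
| 50% | 0.027 | 0.003 | 0.028 |

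None exceeds 0.05.

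**Power, 30 per arm.**

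| HPR rates | Fisher | Split binomial |
|---|---|---|
| 10% vs 2% | 0.043 | 0.043 |
| 15% vs 3% | 0.147 | 0.144 |
| 20% vs 5% | 0.241 | 0.221 |
| 40% vs 10% | 0.705 | 0.594 |
| 50% vs 20% | 0.596 | 0.409 |
| 60% vs 25% | 0.719 | 0.465 |

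The split binomial ignores the patients without HPR. That costs almost nothing when HPR is rare and up to 0.719 − 0.465 = 0.254 in the last row.

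**The case against.** The sentence on categorical tests names neither HPR nor the treatment arms. With five samples per patient, McNemar's test, or its exact binomial form, is correct for within-patient change. A reader might infer that the plan assigns McNemar to the between-arm comparison; the text does not say so, and nothing in the documents suggests pairing patients across arms. That objection stands: what can be shown is an omission. It does not close the gap, because if both tests are for within-patient change, none is left for comparing the arms.

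The endpoint wording also allows a descriptive reading. The PRU items are expressed as differences between the drugs, the HPR item only as rates, and categorical variables are to be summarised as frequencies and percentages. This is possible, though a between-arm comparison is the likelier intent in a randomised comparison of two drugs. If description is all that is meant, the plan should say so.

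The numerical case is also limited. The 13/30 against 5/30 example lies close to Fisher's threshold. At 12/30 against 5/30, Fisher (0.084) and the split binomial (0.143) agree at 0.05. At low HPR rates the power loss nearly vanishes.

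The covariance-model sentence is not an answer. Although it covers all between-group comparisons, its output is a difference in PRU and gives no test of a rate.

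**Conclusion.** The plan names no suitable test for comparing HPR rates between the arms. This follows from the text and needs no assumption about rates. Its size does depend on assumed rates: with 30 per arm, the power lost by using the split binomial rather than Fisher runs from nil (10% vs 2%) to about 25 percentage points (60% vs 25%), and near the threshold the readings can disagree on significance.

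A reader might go further and infer that the plan inflates the false-positive rate. The documents do not support that. Randomly paired McNemar and the split binomial both stay below 0.05. Inflation would require treating one arm's observed rate as a known constant, a use the plan does not describe.

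The point is minor. It affects a secondary endpoint with no stated margin or power, in a study that calls itself a feasibility study. Frequencies and percentages will be reported in any case, and the primary PRU analysis and the 80 patients to be randomised are unaffected.

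**What to change.** Replace the sentence on categorical variables in the Statistical Analysis section with:

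> Between-group comparisons of categorical variables, including HPR at each time point, will use Fisher's exact test. The risk difference will be given with a 95% CI by the Newcombe method as a descriptive estimate; the exact test governs significance. McNemar's test (exact form when discordant pairs are few) will be used only for within-arm changes between time points.

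An exact Cochran-Mantel-Haenszel test stratified by baseline antiplatelet therapy, matching the randomisation, is an acceptable alternative to Fisher if fixed in advance. Another named interval method would also do.

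The wording must say which result governs, because the two can disagree: at 12/30 against 5/30 Fisher gives p = 0.084, while the Newcombe interval for the difference of 0.233 is 0.005 to 0.433 and excludes zero.

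The cost is a short change of text, with no effect on sample size, data collection or the primary analysis. The downside is that Fisher's test is somewhat conservative: its actual type I error is about 0.9% to 2.7% at 30 per arm for assumed HPR of 10% to 50%.
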